#### **9.4.2. Principal Secondary Efficacy Analysis**

The principal secondary endpoint, which is the proportion of subjects whose mean Hgb during the primary efficacy evaluation period is within the target range will be analyzed to demonstrate the superiority of GSK1278863 to epoetin beta pegol in ND subjects.

In the mITT Population, a logistic regression model including treatment group, baseline Hgb, and current ESA therapy (presence or absence) as covariates will be used to estimate the point estimate and 95% CI for the odds ratio (GSK1278863/epoetin beta pegol). This analysis will be performed to demonstrate the superiority at a two-sided significance level of 5%, conditional on the primary endpoint achieving noninferiority. Superiority will be established if the lower limit of the 95% CI for odds ratio is greater than 1.0.

#### **9.4.3. Other Secondary Efficacy Analyses**

Among the secondary efficacy endpoints, the time (%) in Hgb target range during the primary efficacy evaluation period, proportion of subjects who have an Hgb increase of more than 2 g/dL over any 4 weeks, and changes in iron metabolism parameters (ferritin, TSAT, hepcidin, serum iron, and TIBC),

the point estimates and 95% CIs for the treatment difference (or odds ratio) in ND subjects will be calculated. Other secondary efficacy and exploratory endpoints will be summarized by each treatment group.

For PD subjects, the efficacy endpoints will be descriptively summarized.

#### **9.4.4. Safety Analyses**

In principle, safety data will be summarized by each treatment group in the Safety Population. ND subjects and PD subjects will be summarized separately.

##### **9.4.4.1. Exposure**

Exposure information will be listed for all subjects. The duration of treatment (number of days) and cumulative dose will be tabulated. In addition, distribution of the dose level at each assessment visit and final dosing visit will be tabulated. Frequency of dose adjustment and duration of treatment interruption due to Hgb >13 g/dL will be summarized.

##### **9.4.4.2. Adverse Events**

All AEs will be categorized by the MedDRA system organ class and preferred term to tabulate the number and incidence. All AEs, SAEs, AEs leading to discontinuation of study treatment, and AEs of special interest will be summarized separately. Similar summary will be provided for study treatment-related AEs.

##### **9.4.4.3. Other Safety Parameters**

For laboratory tests, vital signs and ECG, parameters and/or changes from baseline will be summarized using summary statistics at each assessment visit. The number and percentage of subjects with values of the potential clinical importance values will be tabulated. The criteria for the potential clinical importance will be described in the RAP. For lipid parameters (total cholesterol, LDL cholesterol, and HDL cholesterol), percent changes will also be tabulated. The number (%) of subjects who have any change in anti-hypertensive medications (type and/or dose) due to increased blood pressure will be tabulated.

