##### **Open-label**

If the study is conducted as a double-blind study, it is necessary to not only administer GSK1278863 orally (once daily) or epoetin beta pegol subcutaneously (once every 2 or 4 weeks), but also administer the matching placebo subcutaneously or orally. It will be more stressful for subjects and complicate treatment procedures to use both active drug and matching placebo for two drugs with different routes and intervals of administration for the purpose of maintaining the blind, and make dose adjustments for individual subjects according to the change in Hgb over time. Accordingly, this study is designed as an open-label study rather than a double-blind study, which seems infeasible. Since Hgb used for efficacy evaluation is an objective measure, and dose adjustments for study medication will be made according to the prespecified Hgb-based dose adjustment method in both GSK1278863 and epoetin beta pegol groups, it is unlikely that the open-label design will create any bias in the primary evaluation.

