## 6.5. Blinding

This is an open-label study.

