## **6.11. Concomitant Medications and Non-Drug Therapies**

Concomitant medications, including over-the-counter medications and supplements, taken during the study will be recorded in the eCRF. Drug names and start/stop dates will be recorded for general concomitant medications, while additional details, including dose, route of administration, and dosing frequency, will be recorded for certain medications (e.g., ESAs, iron, anti-hypertensive medications). Further details are provided in the SRM.

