Potential Risk of Clinical Significance	Summary of Data/Rationale for Risk	Mitigation Strategy
	study between 25mg GSK1278863 with either a CYP2C8 substrate or an OATP1B1/1B3 substrate showed that there is no PK interaction at this dose of GSK1278863.	
provided in Section 6.4.1.
 
 
These risks will be monitored instreamly by the internal safety review team throughout the study period.
 

Other		
ESA risks (Control)	
 
See risks outlined in table for GSK1278863 for Excessive erythropoiesis (polycythemia) leading to thrombosis and/or tissue ischemia; Risk of MI, stroke, thromboembolic events, thrombosis of vascular access; and risk of cancer-related mortality and tumor progression.
 
Non-controllable hypertension
 
Pure red cell aplasia
 
Hepatic function disorder with increase of AST, ALT and Gamma-glutamyltransferase, and jaundice have been reported as adverse drug reactions for other ESA according to the prescribing information of Epoetin beta pegol.
 
	
 
The same mitigation strategies have been indentified in accordance with the mitigation strategies for GSK1278863
 
Blood pressure will be monitored throughout the dosing period as outlined in the Time and Events Table provided in Section 7.1..
 
A criterion to exclude subjects with history of pure red cell aplasia is added to Section 5.2..
 
Liver function will be monitored throughout the dosing period as outlined in the Time and Events Table provided in Section 7.1.
 

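### The one planned count of anti-hypertensive treatment changes depends on an attributed reason in an open-label trial; an all-reason row should stand beside it

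*Protocol*

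**What the plan says.** Section 9.4.4.3 (Other Safety Parameters) commits to the number and percentage of subjects with "any change in anti-hypertensive medications (type and/or dose) due to increased blood pressure". No tabulation of all anti-hypertensive changes is stated there or elsewhere in section 9.4.4.

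Section 6.5 says: "This is an open-label study". The justification for this, in section 4.4, begins "Since Hgb used for efficacy evaluation is an objective measure" and concludes that "it is unlikely that the open-label design will create any bias in the primary evaluation". It makes no claim about safety assessments.

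On data collection, section 6.11 says "Drug names and start/stop dates will be recorded for general concomitant medications", and that "additional details, including dose, route of administration, and dosing frequency, will be recorded for certain medications (e.g., ESAs, iron, anti-hypertensive medications"). The reason for a change is not among the items listed there.

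Appendix 2 (section 12.2) lists "Non-controllable hypertension" under the ESA risks of the control. No GSK1278863 row lists systemic hypertension, and it is not among the adverse events of special interest in section 7.4.2. The stated mitigation is blood-pressure measurement according to the Time and Events Table.

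Other summaries bear on the same risk. Section 9.4.4.3 also summarises vital signs by visit and counts subjects with values of potential clinical importance. Section 9.4.4.2 tabulates all adverse events. Section 9.4.4 presents safety data by treatment group, with ND and PD subjects separate.

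**The concern.** A count of treatment changes is useful because blood pressure is treated during the study: a rise that is promptly treated may leave little trace in the measured values. Here a change enters the count only if somebody says that raised blood pressure was the reason. That person can know the arm, and Appendix 2 names hypertension as a risk of one arm only. The same prescribing decision could then be counted in one arm and left out in the other.

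The protocol's defence of the open-label design does not reach this count. It rests on haemoglobin being objective and is confined to the primary evaluation. Nor does the protocol state whose judgement the reason is or which field holds it, so a reader of the table could not tell how far the two arms were handled alike.

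At stake is the reading of one descriptive safety table in a study intended as pivotal for the Japanese submission.

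**Working it through.** The protocol gives no figure for this count, so there is none to reproduce. The arithmetic shows only how the attribution step acts on the table.

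**Inputs**
- From the protocol: 286 ND subjects for safety analyses (Table 17), randomised 1:1, so 286 / 2 = 143 per arm. This takes all randomised subjects as treated.
- Assumed: the true proportion with an anti-hypertensive change, p, and the share of those changes attributed to raised blood pressure, a. The protocol gives neither.

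**Formulae**
- Counted proportion in an arm: c = p × a.
- Apparent difference: c(control) − c(GSK1278863).
- Standard error: √[c₁(1 − c₁)/143 + c₂(1 − c₂)/143].

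**Same true change rate in both arms, p = 30%**

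| Attribution, control / GSK1278863 | Counted, control v GSK1278863 | Apparent difference (points) | SE (points) |
|---|---|---|---|
| 80% / 80% | 24% v 24% | 0 | 5.1 |
| 80% / 70% | 24% v 21% | 3 | 4.9 |
| 80% / 60% | 24% v 18% | 6 | 4.8 |
| 80% / 50% | 24% v 15% | 9 | 4.7 |
| 70% / 90% | 21% v 27% | −6 | 5.0 |

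Example, second row: 0.30 × 0.80 = 0.24 and 0.30 × 0.70 = 0.21. The SE is √[(0.24 × 0.76 + 0.21 × 0.79)/143] = √(0.3483/143) = 0.049.

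Over true rates from 20% to 50%, attribution of 90% against 80% gives a gap of 2 to 5 points, and 90% against 60% gives 6 to 15 points.

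**A true difference, 40% in control v 30% on GSK1278863**
- Attribution 90% / 90%: 36% v 27%, difference 9 points.
- Attribution 70% / 90%: 28% v 27%, difference 1 point. The real difference has almost disappeared.
- Attribution 90% / 70%: 36% v 21%, difference 15 points. The real difference is exaggerated.

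**Effect of counting every change.** The factor a drops out. Equal true rates then give an expected difference of 0, and 40% v 30% gives 10 points. This removes the attribution step only; p itself is still the result of prescribing with the arm known.

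**Can the all-reason count be built?** Section 6.11 provides drug names, start and stop dates, dose, route and frequency for anti-hypertensives. New agents and dose increases after Day 1 can be derived from these without a reason field.

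**The case against.** The strongest reply is that the hypertension comparison has other support. A reader might infer that the comparison of the arms on this risk depends on attribution. The protocol does not support that: blood pressure by visit, values of potential clinical importance and all adverse events are summarised by arm, and none of them needs a reason for a medication change. This part of the objection stands and confines the point to one table. The other summaries do not fully replace the count, however. Added medication can mask measured blood pressure. Section 7.4.5 takes a single reading, scheduled on treatment after Day 1 at Weeks 4, 16, 28, 40 and 52 (Table 14). An abnormal vital sign is an adverse event only if the investigator judges it clinically significant (section 12.6.1), which is also an unblinded judgement.

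Three further replies have force.
- A reader might assume that the investigator assigns the reason. That is plausible, but the protocol does not say so, and the analysis plan, which is not shown, may define it.
- A reader might infer a bias in favour of GSK1278863 because Appendix 2 names hypertension for the control. Sites could equally be more alert to blood pressure on a new agent, so the direction is not established.
- The restriction has a purpose: it leaves out changes made for other indications. An all-reason count lets these in and may dilute a real difference.

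It is also fair to say that no test is planned on this count, and that the largest gap in the 80% attribution examples, 9 points, is about 1.9 standard errors (9 / 4.7).

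What does not stand is that this is purely a matter for the analysis plan. The protocol itself fixes the restricted count and states no other tabulation of blood-pressure treatment.

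**Conclusion.** The point holds in a limited form. The only stated tabulation of blood-pressure treatment is conditional on a reason that is assigned in an open-label trial and has no stated source. Differential attribution could create or hide a difference between arms in that table, in either direction.

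The illustrated size is 3 to 9 points at an assumed true rate of 30% with 80% attribution in control, or 2 to 15 points over the wider range, against standard errors of roughly 4 to 6 points at 143 per arm. Every rate and share behind these figures is an assumption, so they show what could happen and are not an estimate. There is no contradiction within the protocol, since its open-label defence claims only the primary evaluation. No efficacy conclusion is affected. The matter is a worthwhile improvement to one descriptive safety table.

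**What to change.** In section 9.4.4.3, add by treatment group the number and percentage of subjects with any new anti-hypertensive agent or any anti-hypertensive dose increase after Day 1, whatever the stated reason, derived from the medication record collected under section 6.11. Keep the count attributed to raised blood pressure as a second row. State who assigns the reason and where it is recorded.

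The cost is one extra table row and a sentence of definition, with no new data and no change to patient management. The downside is that the all-reason row includes changes made for other indications, which may dilute a real difference, and it still reflects unblinded prescribing. It is therefore not a fully objective replacement, and the two rows should be read together and alongside the measured blood pressure.

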#### **9.4.5. Pharmacokinetics Analyses**

For plasma concentrations of GSK1278863 over time, individual data will be listed, and summary statistics at each time point will be calculated for each dose level. For PK parameters (AUC0-4 and Cmax), summary statistics will be calculated for each dose level, and scatter plots against the dose level will be generated.

#### **9.4.6. PRO Data Analysis**

Details of PRO data tabulation will be described in the RAP.

## 10. STUDY GOVERNANCE CONSIDERATIONS

### 10.1. Posting of Information on Publicly Available Clinical Trial Registers

Study information from this protocol will be posted on publicly available clinical trial registers before enrollment of subjects begins.

### 10.2. Regulatory and Ethical Considerations, Including the Informed Consent Process

The study will be conducted in accordance with “the Ministerial Ordinance on the Standards for the Conduct of Clinical Trials of Medicinal Products (MHW Notification No.28 dated 27th March, 1997)” and the Pharmaceutical Affairs Law.

GSK will submit the CTN to the regulatory authorities in accordance with Article 80-2 of the Pharmaceutical Affairs Law before conclusion of any contract for the conduct of the study with study sites.

The study will be conducted in accordance with all applicable regulatory requirements, and with GSK policy.

The study will also be conducted in accordance with ICH Good Clinical Practice (GCP), all applicable subject privacy requirements, and the guiding principles of the current version of the Declaration of Helsinki. This includes, but is not limited to, the following:

- IRB/IEC review and favorable opinion/approval of the study protocol and amendments as applicable
- Signed informed consent to be obtained for each subject before participation in the study (and for amendments as applicable)
- Investigator reporting requirements (e.g. reporting of AEs/SAEs/protocol deviations to IRB/IEC)
- GSK will provide full details of the above procedures, either verbally, in writing, or both.
- The IEC/IRB, and where applicable the regulatory authority, approve the clinical protocol and all optional assessments, including genetic research.
- Optional assessments (including those in a separate protocol and/or under separate informed consent) and the clinical protocol should be concurrently submitted for approval unless regulation requires separate submission.
- Approval of the optional assessments may occur after approval is granted for the clinical protocol where required by regulatory authorities. In this situation, written approval of the clinical protocol should state that approval of optional assessments is being deferred and the study, with the exception of the optional assessments, can be initiated.

#### **Informed Consent**

Prior to participation in the study, the investigator (or subinvestigator) should fully inform the potential subject and the subject's legally acceptable representative (as required) of the study including the written information. The investigator (or subinvestigator) should provide the subject and the subject's legally acceptable representative ample time and opportunity to inquire about details of the study. The subject and the subject's legally acceptable representative should sign and personally date the consent form. If the subject wishes to consider the content of the written information at home,

he/she may take the consent form home. The person who conducted the informed consent discussion and study collaborator giving supplementary explanation, where applicable, should sign and personally date the consent form. If an impartial witness is required, the witness should sign and personally date the consent form. The investigator (or subinvestigator) should retain this signed and dated form (and other written information) together with the source medical records, such as clinical charts (in accordance with the rules for records retention, if any, at each medical institution) and give a copy to the subject and the subject's legally acceptable representative.

### **10.3. Quality Control (Study Monitoring)**

In accordance with applicable regulations including GCP, and GSK procedures, GSK monitors will contact the site prior to the start of the study to review with the site staff the protocol, study requirements, and their responsibilities to satisfy regulatory, ethical, and GSK requirements. When reviewing data collection procedures, the discussion will also include identification, agreement and documentation of data items for which the CRF will serve as the source document.

GSK will monitor the study and site activity to verify that the:

- Data are authentic, accurate, and complete.
- Safety and rights of subjects are being protected.
- Study is conducted in accordance with the currently approved protocol and any other study agreements, GCP, and all applicable regulatory requirements.

The investigator and the head of the medical institution (where applicable) agrees to allow the monitor direct access to all relevant documents

### **10.4. Quality Assurance**

To ensure compliance with GCP and all applicable regulatory requirements, GSK may conduct a quality assurance assessment and/or audit of the site records, and the regulatory agencies may conduct a regulatory inspection at any time during or after completion of the study.

In the event of an assessment, audit or inspection, the investigator (and institution) must agree to grant the advisor(s), auditor(s) and inspector(s) direct access to all relevant documents and to allocate their time and the time of their staff to discuss the conduct of the study, any findings/relevant issues and to implement any corrective and/or preventative actions to address any findings/issues identified.

### **10.5. Study and Site Closure**

Upon completion or premature discontinuation of the study, the GSK monitor will conduct site closure activities with the investigator or site staff, as appropriate, in accordance with applicable regulations including GCP, and GSK Standard Operating Procedures.

GSK reserves the right to temporarily suspend or prematurely discontinue this study at any time for reasons including, but not limited to, safety or ethical issues or severe non-compliance. For multicenter studies, this can occur at one or more or at all sites.

If GSK determines such action is needed, GSK will discuss the reasons for taking such action with the investigator or the head of the medical institution (where applicable). When feasible, GSK will provide advance notification to the investigator or the head of the medical institution, where

applicable, of the impending action.

If the study is suspended or prematurely discontinued for safety reasons, GSK will promptly inform all investigators, heads of the medical institutions (where applicable) and/or institution(s) conducting the study. GSK will also promptly inform the relevant regulatory authorities of the suspension or premature discontinuation of the study and the reason(s) for the action.

If required by applicable regulations, the investigator or the head of the medical institution (where applicable) must inform the IRB/IEC promptly and provide the reason for the suspension or premature discontinuation.

## **10.6. Records Retention**

Following closure of the study, the investigator or the head of the medical institution (where applicable) must maintain all site study records (except for those required by local regulations to be maintained elsewhere), in a safe and secure location.

The records must be maintained to allow easy and timely retrieval, when needed (e.g., for a GSK audit or regulatory inspection) and must be available for review in conjunction with assessment of the facility, supporting systems, and relevant site staff.

Where permitted by local laws/regulations or institutional policy, some or all of these records can be maintained in a format other than hard copy (e.g., microfiche, scanned, electronic); however, caution needs to be exercised before such action is taken. The investigator must ensure that all reproductions are legible and are a true and accurate copy of the original and meet accessibility and retrieval standards, including re-generating a hard copy, if required. Furthermore, the investigator must ensure there is an acceptable back-up of these reproductions and that an acceptable quality control process exists for making these reproductions.

GSK will inform the investigator of the time period for retaining these records to comply with all applicable regulatory requirements. The minimum retention time will meet the strictest standard applicable to that site for the study, as dictated by any institutional requirements or local laws or regulations, GSK standards/procedures, and/or institutional requirements.

The investigator must notify GSK of any changes in the archival arrangements, including, but not limited to, archival at an off-site facility or transfer of ownership of the records in the event the investigator is no longer associated with the site.

## **10.7. Provision of Study Results to Investigators, Posting of Information on Publicly Available Clinical Trials Registers and Publications**

Where required by applicable regulatory requirements, an investigator signatory will be identified for the approval of the clinical study report. The investigator will be provided reasonable access to statistical tables, figures, and relevant reports and will have the opportunity to review the complete study results at a GSK site or other mutually-agreeable location.

GSK will also provide the investigator with the full summary of the study results. The investigator is encouraged to share the summary results with the study subjects, as appropriate.

The procedures and timing for public disclosure of the results summary and for development of a manuscript for publication will be in accordance with GSK Policy.

